2.3 Proposed next step

The goal of the proposed studies is to test the preliminary efficacy of LACTIN-V in recurrent UTI, as well as to confirm previous safety data. The pre-filled vaginal applicator delivery system will be employed for LACTIN-V as a powder formulation of *Lactobacillus crispatus* CTV-05 provided at a dose of 600 mg (containing 2×10^9 CFU of *L. crispatus* CTV-05 per dose), as in published trials using LACTIN-V for BV (15, 16).

3 STUDY PURPOSE, OBJECTIVES AND ENDPOINTS

3.1 Purpose

The purpose of this study is to evaluate the efficacy and safety of *Lactobacillus crispatus* strain CTV-05 (LACTIN-V) in pre-menopausal women with uncomplicated recurrent urinary tract infection (RUTI). The purpose, objectives, endpoints, and design of this study will be similar to the completed Phase 2 study of the safety and preliminary efficacy of LACTIN-V (13).

3.2 Study Objectives

3.2.1 Primary Objective

The primary objective of this study is to evaluate the efficacy of LACTIN-V, compared to placebo, in pre-menopausal women with recurrent uncomplicated UTI.

1. To evaluate the number (percent) of subjects in each treatment group with at least one recurrence of symptomatic UTI.
2. To evaluate the efficacy of LACTIN-V, compared to placebo, in reducing the incidence of symptomatic UTI.
3. To evaluate the time to recurrence, in subjects receiving LACTIN-V as compared to placebo, of symptomatic UTI

3.2.2 Secondary Objectives

1. To evaluate vaginal colonization with total *Lactobacillus* (endogenous and exogenous) in subjects receiving LACTIN-V versus placebo.
2. To evaluate vaginal colonization with *Lactobacillus crispatus* strain CTV-05 (the LACTIN-V strain of *Lactobacillus*).
3. To evaluate vaginal colonization with *E. coli* in subjects receiving LACTIN-V versus placebo.
4. To evaluate shifts in vaginal microbiota in subjects receiving LACTIN-V versus placebo, as assessed by Nugent score of vaginal gram stains at all visits.

5. To evaluate shifts in the composition of vaginal microbiota in subjects receiving LACTIN-V versus placebo, as assessed by qualitative and/or quantitative DNA amplification of stored vaginal fluid specimens from all visits.
6. To evaluate the safety of LACTIN-V over four months.

3.3 Case Definitions

3.3.1 Symptomatic UTI

Symptomatic UTI is defined as an episode with one or more UTI symptoms (dysuria, urgency, frequency) prompting evaluation and treatment, with a positive urine culture. A positive urine culture is defined as $\geq 10^2$ /ml of an uropathogen in these patients.

3.3.2 Probable UTI

Probable UTI is defined as an episode with one or more UTI symptoms (dysuria, urgency, frequency) prompting evaluation and treatment. This can occur in the absence of a MSU culture.

3.3.3 Recurrent UTI

In this study, for the purpose of eligibility, the diagnosis of recurrent UTI is defined as one or more symptomatic, treated UTIs in the prior 12 months.

3.4 Study Endpoints

3.4.1 Primary Endpoint

The primary endpoint of this study is to demonstrate the efficacy of *Lactobacillus crispatus* strain CTV-05 (LACTIN-V) in pre-menopausal women with RUTI, when administered vaginally at a dose of 2×10^9 CFU once per day for five consecutive days followed by once per week for 8 weeks, for preventing RUTI.

3.4.2 Secondary Endpoints

To evaluate changes in the vaginal environment and determine the extent of colonization of CTV-05 over the course of the study and to assess AE's reported by subjects or thru physical exam by investigators.

4 RATIONALE

4.1 Overview

The goal of this Phase 3 study is to obtain preliminary data on LACTIN-V's ability to reduce the UTI recurrence rate, decrease UTI incidence and/or increase time to first UTI recurrence in pre-menopausal women who have a history of recurrent uncomplicated UTI, and to continue to evaluate the safety of LACTIN-V. LACTIN-V will be administered at a dose of 5×10^9 CFU of *L. crispatus* strain CTV-05/powder applicator once daily for five consecutive days then once per week for the following 10 weeks. Subjects will be followed off LACTIN-V or placebo for an additional 10 weeks following this dosing regimen for recurrent UTI, vaginal microbiota measures, and AEs.

4.2 Rationale for Dose and Regimen

LACTIN-V is available in a dose level of 5×10^9 CFU/applicator for this Phase 3 study in the rUTI population, which is the same dose studied in a Phase 1 Study and a Phase 2a BV study (Protocols LV-005 and LV-006, respectively). No serious adverse events have been reported.

Preliminary data from Protocol LV-001 have shown that subjects receiving LACTIN-V at the 5×10^8 CFU/capsule dose level had a 40% colonization rate (6/15 subjects) with the *L. crispatus* strain CTV-05, as compared to a 20% colonization rate (3/15 subjects) in the 5×10^6 CFU/capsule treatment group (Osel Inc., personal communication). At a dose of 2×10^9 CFU/applicator (Protocol LV-006), 61% of women randomized to the LACTIN-V group were colonized with *L. crispatus* CTV-05 at Day 10 or Day 28. Among LACTIN-V users with complete adherence to the study regimen, 78% were colonized at Day 10 or Day 28.

The dosing regimen selected for this study was based on the dosing regimen in the Phase 1 and 2a studies with LACTIN-V, in which subjects inserted one capsule daily for five consecutive days, followed by one applicator weekly for 2 weeks. In this Phase 3 study, as in Protocol UW/LB-001, subjects will receive one intravaginal applicator daily for five consecutive days (Days 1–5), followed by one applicator weekly for 10 weeks (starting on Day 8) for a total of 15 applicators over 11 weeks. Weekly dosing has been added for 10 weeks following the initial five-day course so that *L. crispatus* strain CTV-05 colonization can be maintained throughout the study period.

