5 STUDY DESIGN

5.1 Description of the Study

This is a Phase 3, randomized, double-blind, placebo-controlled study. Safety will be assessed using self-reported symptoms, pelvic examinations and vaginal cultures. The study will be conducted in 276 women with UTI symptoms and a history UTI in the past 12 months. The duration of the antibiotic course prior to study entry is anticipated to be 3–5 days, however the length of treatment will be decided by the treating provider.

At the Screening Visit (Visit 0), subjects will be evaluated for eligibility with a medical history, physical examination, genital examination and vaginal swabs for specimen collection.

If found eligible based on the results of the Screening Visit (v0), the subject will be prescribed antibiotics and scheduled to return for the randomization visit in 3-10 days after antibiotic completion. At Visit 1 subject will be randomized to receive either LACTIN-V at a dose of 5×10^9 CFU/applicator daily for five days followed by one applicator per week for 8 weeks or the placebo applicator on the same schedule. The LACTIN-V applicator will contain active *Lactobacillus* (strain CTV-05) in maltodextrin and a preservation matrix and the placebo capsule will contain maltodextrin and preservation matrix only. LACTIN-V is supplied as a powder formulation in a pre-filled, single-use applicator. The preservation matrix contains xylitol, trehalose, and sodium ascorbate. LACTIN-V placebo applicators contain 200 mg of the powder formulation without *L. crispatus* CTV-05.

Visit 0 (Screening Visit) will occur at the time of the UTI diagnosis. Visit 1 should occur within 3–10 days of completing antibiotic. Visit 2 will occur at Week 3, Visit 3 at Week 6, and visits will be monthly thereafter for 3 months.

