At Visit 1, each subject who continues to meet all inclusion and exclusion criteria will be randomized and will receive a box containing 15 applicators. Two extra applicators will be kept at the study site in case a lost or damaged applicator needs to be replaced. The first study applicator will be inserted under supervision in clinic at this visit. The remaining 14 applicators will be inserted daily at bedtime on Days 2–5, and then weekly. Women are to abstain from sexual intercourse and tampon use for 24 hours after each applicator is used. If the subject's partner uses condoms, they will be instructed to use non-spermicidal condoms to avoid killing the *L. crispatus*. The use of other intravaginal products including douching is prohibited throughout the four-month study period. Subjects must agree not to self-medicate with antibiotics or antifungals during the four-month study period. However, subjects may be treated for any on-study vaginal or other infection if a health care provider deems such treatment necessary. Subjects who receive antibiotic or antifungal treatment after commencing the study should continue to insert the study applicator according to their allocated schedule.

Subjects will be provided with a Study Diary to use to record applicator use information during the study. The Study Diary will also be used by subjects to record any symptoms. Subjects will be instructed on how to use these memory aids to remind them to insert the applicator on the designated day and to record the date and time when each applicator was inserted.

Self-reported symptoms will be evaluated at all study visits. Subjects will be queried about the following symptoms:

Nausea or vomiting
Abdominal Discomfort
Diarrhea
Constipation
Rash
Abnormal Vaginal Discharge/Bleeding
Abnormal Vaginal Odor
Genital itching or burning
External genital irritation/swelling
Painful Urination
Urinary Frequency
Urinary Urgency
Blood in urine

Headache
Other: _____

Other: _____

Subjects will be instructed to call the study clinic if they have any unexpected symptoms at any time during the study.

Pelvic examinations will be performed at all visits to evaluate the external genitalia; cervix and vaginal mucosa for signs of irritation at Visits 1 and 6 and if clinically indicated.

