6.7 Lost Applicators

Extra applicators will be provided to each subject together with the required 13 applicators. If a subject loses or damages a study applicator, she may take one of the extras provided, as long as the total number of applicators used does not exceed 13. Lost or damaged applicators should be documented on the Study Diary.

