10 STATISTICAL CONSIDERATIONS

10.1 Primary Endpoint

The primary endpoint of this Phase 2 study is to evaluate the efficacy of *Lactobacillus crispatus* strain CTV-05 (LACTIN-V) in pre-menopausal women who have a history of recurrent uncomplicated UTI when the product is administered vaginally at a dose of 2 x 10⁹ CFU/capsule once per day for five consecutive days followed by once per week for 10 weeks. The main analysis of interest will be the comparison of UTI during the follow-up period, looking at:

1. UTI incidence over the 16-week study period in the LACTIN-V treatment group (Group A) as compared to the placebo group (Group B) of:
 - a. Symptomatic or Probable UTI
 - b. Symptomatic UTI
2. Time to recurrence, as measured from date of the Randomization Visit (Day 1) to the date of first UTI diagnosis post-randomization, in the LACTIN-V group (Group A) compared to the placebo group (Group B) of:
 - a. Symptomatic or Probable UTI
 - b. Symptomatic UTI
3. Comparison of the number (%) of subjects over the 16-week study period with at least one:
 - a. Symptomatic or Probable UTI
 - b. Symptomatic UTI

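### The protocol gives two strengths (2 × 10^9 and 5 × 10^9 CFU), two weekly phases (8 and 10 weeks) and two applicator totals (13 and 15), and section 4.2 misstates the dose studied in LV-005 and LV-006

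*Combined protocol and SAP*

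**What the plan says.** The statements on the regimen, all from current operative text, are these:

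| Section | Strength (CFU) | Weekly phase | Applicators |
|---|---|---|---|
| 2.3 | 2 × 10^9 | – | – |
| 3.4.1 (primary endpoint) | 2 × 10^9 | 8 weeks | – |
| 4.1 | 5 × 10^9 | 10 weeks | – |
| 4.2 | 5 × 10^9 | 10 weeks | 15 over 11 weeks |
| 4.3 | 5 × 10^9 | – | – |
| 5.1, regimen sentence | 5 × 10^9 | 8 weeks | – |
| 5.1, dispensing at Visit 1 | – | – | 15, all inserted |
| 6.1.1 | 2 × 10^9 | – | – |
| 6.7 | – | – | 13, required and maximum |
| 10.1 (statistical section) | 2 × 10^9 | 10 weeks | – |
| Flow chart | – | 10 weeks | – |

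Section 3.4.1 specifies dosing "once per day for five consecutive days followed by once per week for 8 weeks"; section 10.1 specifies "once per day for five consecutive days followed by once per week for 10 weeks". Section 5.1 first describes LACTIN-V "daily for five days followed by one applicator per week for 8 weeks or the placebo applicator on the same schedule". It then says that each woman "will be randomized and will receive a box containing 15 applicators", and after the first is used in clinic, "The remaining 14 applicators will be inserted daily at bedtime on Days" 2–5 and then weekly. On spares it says "Two extra applicators will be kept at the study site in case a lost or damaged applicator needs to be replaced". Section 6.7 instead gives each woman extras "together with the required 13 applicators" and does not let total use go above that number.

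On precedent, section 4.2 describes 5 × 10^9 as the dose "which is the same dose studied in a Phase 1 Study and a Phase 2a BV study (Protocols LV-005 and LV-006, respectively") and follows this with a statement that no serious adverse events have been reported.

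**The concern.** The primary endpoint is efficacy of a named dose given for a named period, so a conflict in either figure leaves the tested intervention undefined. Sections 3.4.1, 5.1 (regimen sentence) and 10.1 name three different regimens, and 4.1 and 4.2 supply the fourth combination.

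The two conflicts have different consequences. Applicators are pre-filled and prepackaged, so a site cannot choose a strength. The CFU conflict is therefore an error in the record of what is given, and in the argument that the dose has been used safely before. The schedule conflict bears on conduct: how many applicators a woman is told to insert, whether staff stop at the 6.7 cap, and what counts as full dosing for the ATP cohort. Section 10.7 limits that cohort to women who satisfy every protocol specification and uses it for the primary endpoints.

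**Working it through.** **1. The figure in 4.2.** Total doses = 5 daily + w weekly. With weekly dosing from Day 8, the last dose falls on Day 8 + 7(w − 1). For w = 10: 5 + 10 = 15 doses, last on Day 8 + 63 = Day 71, in week 11. This reproduces the 15 applicators over 11 weeks in 4.2.

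**2. The same count for 8 weeks.** For w = 8: 5 + 8 = 13 doses, last on Day 8 + 49 = Day 57, in week 9. This is the 13 in 6.7. (Section 4.2 gives the Day 8 start only for the 10-week schedule; applying it to 8 weeks is an assumption.)

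**3. Section 5.1 against itself.** Box of 15 − 1 in clinic = 14; 14 − 4 on Days 2–5 = 10 weekly doses. The regimen sentence in the same section gives 8.

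**4. Can 13 and 15 be reconciled as doses plus spares?**
- Reading A: 13 required + 2 spares = a box of 15. This fits 6.7, 3.4.1, the 5.1 regimen sentence and Appendix B, which asks a woman to call if more than two are lost. It does not fit the rest of 5.1, where all 15 in the box are inserted and the two spares stay at the site, nor 4.2, where 15 is the dosing total.
- Reading B: 15 to insert + 2 held at the site = 17 supplied. This fits 4.2, the dispensing text of 5.1, 10.1 and the flow chart. It does not fit 3.4.1, the 5.1 regimen sentence or 6.7. Section 10.1 is a weak witness because it still calls the study Phase 2 and the product a capsule.

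Neither reading fits all the text.

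**5. The precedent for 5 × 10^9.** From section 2.2.2.2:
- LV-005 had three blocks of 4, at 5 × 10^8, 1 × 10^9 and 2 × 10^9, randomized 3:1, so 3 women were assigned active product at 2 × 10^9.
- LV-006 had 18 women randomized to LACTIN-V at 2 × 10^9.
- Total: 3 + 18 = 21 assigned 2 × 10^9 and 0 assigned 5 × 10^9.

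The next paragraph of 4.2 itself gives 2 × 10^9 for LV-006.

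**6. Size of the strength conflict.** 5 × 10^9 / 2 × 10^9 = 2.5. Planned cumulative exposure ranges from 13 × 2 × 10^9 = 2.6 × 10^10 to 15 × 5 × 10^9 = 7.5 × 10^10 CFU, a ratio of 2.9.

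**7. Time off product.** Assumptions: weeks counted from Day 1, no deferred doses. Week 16 (last visit in 4.3) is Day 113; Week 18 (last visit in 10.3 and the flow chart) is Day 127.

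| Weekly doses | Last dose | Off product to Week 16 | Off product to Week 18 |
|---|---|---|---|
| 8 | Day 57 | 56 days (8 weeks) | 70 days (10 weeks) |
| 10 | Day 71 | 42 days (6 weeks) | 56 days (8 weeks) |

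Section 4.1 pairs 10 weekly doses with 10 weeks off product: Day 71 + 70 = Day 141, or Week 20, beyond both calendars. Its 10 weeks off product fits Week 18 only with 8 weekly doses.

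**The case against.** The best reply is that this is largely clerical. If the 5 in 4.1, 4.2, 4.3 and 5.1 is a repeated slip for 2, the strength conflict and the false precedent are one error, and the safety point disappears unless 5 × 10^9 is really supplied. That is plausible, and the weight of the text does favour 2 × 10^9. But the slip would have to occur in four sections, and the sentence in 4.2 is wrong as it stands whichever strength is in the applicator. The support is also not clean: for the same 2 × 10^9 CFU, 2.3 gives a fill of 600 mg and 6.1.1 gives 200 mg.

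On the schedule, 10 weeks has the better stated rationale. Section 4.2 says it follows UW/LB-001, which section 2.2.2.2 describes as five daily doses then 10 weekly ones, and no reason is given for 8 weeks. This stands as evidence of intent, but it does not remove the 8 weeks from the primary endpoint or the 13 from 6.7.

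The practical consequences are modest. Staff mark each woman's dosing dates, recruitment is described at one centre, and a single schedule would probably reach both blinded arms. Section 10.7 sets no dose count for the ATP cohort, so the effect there is inferred. The 6.7 cap matters only when a woman on a 15-dose schedule needs a replacement. She could then finish one dose short if only the replacement is refused, or two short if use is stopped at 13. Her own instructions in Appendix B carry no cap. These points limit the severity; none reconciles the text.

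**Conclusion.** The concern holds: the regimen is wrong as written. Strength conflicts 2.5-fold, the dose count is 13 or 15, and supply including spares is 15 or 17 per woman. The precedent claimed in 4.2 for 5 × 10^9 has no support in the protocol's accounts of LV-005 and LV-006. If 5 × 10^9 is supplied, it is 2.5 times the highest dose reported for those studies; if 2 × 10^9 is supplied, four sections carry the wrong dose.

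The documents point to 2 × 10^9 for strength but do not settle the weekly duration. These contradictions rest on direct reading and simple counts; only the off-product intervals depend on the Day 8 start and no deferred doses. The matter should be corrected, but it does not by itself threaten the MITT comparison or the power, provided both arms follow one schedule.

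**What to change.** 1. **Strength.** State the one strength actually supplied in 2.3, 3.4.1, 4.1–4.3, 5.1, 6.1.1 and 10.1. Reconcile the 600 mg and 200 mg fill weights in the same amendment.
2. **Precedent.** Correct the sentence in 4.2. If 5 × 10^9 is supplied, say that it is 2.5 times the highest dose reported for LV-005 and LV-006.
3. **Duration.** The sponsor should declare the intended weekly phase: 8 weeks (13 doses) or 10 weeks (15 doses).
4. **Alignment.** Bring into line with that choice 3.4.1, 4.1, 4.2, 5.1, 10.1 and the flow chart; the box contents and where spares are held; the required number and cap in 6.7; and the planned dose count for ATP membership. Adopt one visit calendar and restate the off-product period in 4.1 to match it.

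The cost is amendment wording, with no added patients, visits or procedures.

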4.3 Rationale for Study Design

The study will enroll 276 pre-menopausal women currently with a symptomatic UTI who report at least one other symptomatic UTI episode treated within the past 12 months. Subjects will be randomized to receive either LACTIN-V (5×10^9 CFU/applicator) or a placebo applicator in a 1:1 ratio. The Randomization Visit (Visit 1) must occur within 3–

10 days of completing antibiotics since the vaginal microbiota is thought to be maximally disrupted at this time, thus providing *L. crispatus* CTV-05 the best chance of successful colonization.

It is not anticipated that the entry UTI episode will necessarily have fully resolved at the time of randomization (Visit 1), as mild symptoms may still be present, and the dipstick and urinalysis may still be positive or equivocal several days after completing antibiotics. However, the urine culture is anticipated to be negative at Visit 1, following completion of antibiotics; therefore, subjects with a positive urine culture at this visit will be considered an antibiotic treatment failure.

All subjects will return to clinic at 2, 4, 8, 12, and 16 weeks to assess efficacy and safety. Colonization with *L. crispatus* CTV-05 and other lactobacilli, as well as *E. coli*, will be assessed at all visits. Nugent scores will be determined at baseline and all subsequent visits to evaluate vaginal microbiota pre- and post-treatment.

4.4 Rationale for Study Endpoints

4.4.1 Efficacy

Preliminary efficacy will be assessed by evaluating subjects for Symptomatic UTI. Subjects will also be queried at each visit for any UTI symptoms occurring since the prior visit. In addition, subjects will be instructed to return to clinic for an additional visit if they develop symptoms of UTI during the four-month study period.

4.4.2 Safety

Safety will be evaluated using the following safety measures:

1. Subjects will be queried about adverse events at all visits.
2. Subjects will be given a Study Diary to record symptoms.
3. Genital examinations at all visits. Complete pelvic exams at visit one and six or if clinically indicated.

4.4.3 *Lactobacillus* Colonization

Vaginal colonization with lactobacilli will be assessed by vaginal culture. This culture information will be both specific to *L. crispatus* CTV-05 and non-specific (total vaginal lactobacilli, including endogenous and exogenous lactobacilli).

Total *Lactobacillus* colonization and H₂O₂ production will be assessed using culture. Colonization specifically with *L. crispatus* CTV-05 will be assessed using a DNA fingerprinting technique known as rep-PCR (11), a repetitive element sequence-based PCR, which will be used to identify the specific strain of *L. crispatus* (CTV-05) by

amplifying its unique pattern of DNA fragments. This technique, which makes use of repetitive sequences dispersed throughout a bacterial genome for the direct amplification of genomic DNA, generates bacterial species- or strain-specific fingerprint patterns. Rep-PCR can be used to distinguish probiotic *L. crispatus* strain CTV-05 from other *L. crispatus* species. The *Lactobacillus* cultures and CTV-05 rep-PCR will be performed in the lab of [name]. at the University of Washington. The rep-PCR data collected will be used to assess the correlation between colonization and clinical endpoints.

Vaginal fluid specimens will be stored from each visit for analysis of shifts in the composition of vaginal microbiota by qualitative and/or quantitative DNA amplification methods. DNA amplification will be performed in the lab of [name] M.D. at the University of Washington.

4.4.4 *E. coli* Colonization

Vaginal colonization with *E. coli* will be assessed by vaginal culture at all visits. The *E. coli* cultures will be performed in the lab of [name]. at the University of Washington.

5 STUDY DESIGN

5.1 Description of the Study

This is a Phase 3, randomized, double-blind, placebo-controlled study. Safety will be assessed using self-reported symptoms, pelvic examinations and vaginal cultures. The study will be conducted in 276 women with UTI symptoms and a history UTI in the past 12 months. The duration of the antibiotic course prior to study entry is anticipated to be 3–5 days, however the length of treatment will be decided by the treating provider.

At the Screening Visit (Visit 0), subjects will be evaluated for eligibility with a medical history, physical examination, genital examination and vaginal swabs for specimen collection.

If found eligible based on the results of the Screening Visit (v0), the subject will be prescribed antibiotics and scheduled to return for the randomization visit in 3-10 days after antibiotic completion. At Visit 1 subject will be randomized to receive either LACTIN-V at a dose of 5×10^9 CFU/applicator daily for five days followed by one applicator per week for 8 weeks or the placebo applicator on the same schedule. The LACTIN-V applicator will contain active *Lactobacillus* (strain CTV-05) in maltodextrin and a preservation matrix and the placebo capsule will contain maltodextrin and preservation matrix only. LACTIN-V is supplied as a powder formulation in a pre-filled, single-use applicator. The preservation matrix contains xylitol, trehalose, and sodium ascorbate. LACTIN-V placebo applicators contain 200 mg of the powder formulation without *L. crispatus* CTV-05.

Visit 0 (Screening Visit) will occur at the time of the UTI diagnosis. Visit 1 should occur within 3–10 days of completing antibiotic. Visit 2 will occur at Week 3, Visit 3 at Week 6, and visits will be monthly thereafter for 3 months.

At Visit 1, each subject who continues to meet all inclusion and exclusion criteria will be randomized and will receive a box containing 15 applicators. Two extra applicators will be kept at the study site in case a lost or damaged applicator needs to be replaced. The first study applicator will be inserted under supervision in clinic at this visit. The remaining 14 applicators will be inserted daily at bedtime on Days 2–5, and then weekly. Women are to abstain from sexual intercourse and tampon use for 24 hours after each applicator is used. If the subject's partner uses condoms, they will be instructed to use non-spermicidal condoms to avoid killing the *L. crispatus*. The use of other intravaginal products including douching is prohibited throughout the four-month study period. Subjects must agree not to self-medicate with antibiotics or antifungals during the four-month study period. However, subjects may be treated for any on-study vaginal or other infection if a health care provider deems such treatment necessary. Subjects who receive antibiotic or antifungal treatment after commencing the study should continue to insert the study applicator according to their allocated schedule.

Subjects will be provided with a Study Diary to use to record applicator use information during the study. The Study Diary will also be used by subjects to record any symptoms. Subjects will be instructed on how to use these memory aids to remind them to insert the applicator on the designated day and to record the date and time when each applicator was inserted.

Self-reported symptoms will be evaluated at all study visits. Subjects will be queried about the following symptoms:

Nausea or vomiting
Abdominal Discomfort
Diarrhea
Constipation
Rash
Abnormal Vaginal Discharge/Bleeding
Abnormal Vaginal Odor
Genital itching or burning
External genital irritation/swelling
Painful Urination
Urinary Frequency
Urinary Urgency
Blood in urine

Headache
Other: _____

Other: _____

Subjects will be instructed to call the study clinic if they have any unexpected symptoms at any time during the study.

Pelvic examinations will be performed at all visits to evaluate the external genitalia; cervix and vaginal mucosa for signs of irritation at Visits 1 and 6 and if clinically indicated.

In addition to safety, this study will evaluate the efficacy of LACTIN-V in reducing the incidence of Symptomatic UTI. Subjects will be queried at each clinic visit for urinary symptoms, including dysuria, frequency, urgency, hematuria, flank pain or suprapubic pain. Urinary dipstick, urinalysis and urine culture will be performed at each clinic visit. Subjects will be asked to return to clinic as soon as possible if they develop symptoms of UTI during the four-month study period.

